**Table 2. Specific Toxicity Management Guidelines for Abnormal Laboratory Values**

	Laboratory Parameter	Value	Toxicity Management Guideline
All Subjects	Hemoglobin	< 8 g/dL	
 
• If alternative etiology cannot be identified, interrupt study drug dosing and redraw lab with a new sample.
 
• If value is confirmed, continue to withhold study drug until value returns to normal reference range or baseline value.
 

		Decrease $\geq 3.0$ g/dL from baseline	
 
• If an alternative etiology is known or the hemoglobin value remains in the normal reference range, the subject may continue study drug dosing at the investigator's discretion.
 
• If alternative etiology cannot be identified, interrupt study drug dosing and redraw lab with a new sample.
 
• If value is confirmed, continue to withhold study drug until value returns to normal reference range or baseline value.
 

	Absolute neutrophil count (ANC)	< 1000 cells/ $\mu$ L	
 
• Interrupt study drug dosing and redraw lab with a new sample.
 
• If value is confirmed, continue to withhold study drug until value returns to normal reference range or baseline value.
 

		< 500 cells/ $\mu$ L	
 
• Interrupt study drug dosing and redraw lab with a new sample.
 
• If value is confirmed, discontinue study drug.
 

	Absolute lymphocyte counts (ALC)	< 500 cells/ $\mu$ L	
 
• Interrupt study drug dosing and redraw lab with a new sample.
 
• If value is confirmed, continue to withhold study drug until value returns to normal reference range or baseline value.
 

	Total white blood cell count	< 2,500 cells/ $\mu$ L	
 
• Interrupt study drug dosing and redraw lab with a new sample.
 
• If value is confirmed, continue to withhold study drug until value returns to normal reference range or baseline value.
 

	Laboratory Parameter	Value	Toxicity Management Guideline
All Subjects (continued)	Platelet count	< 50,000 cells/ $\mu$ L	
 
Interrupt study drug dosing and redraw lab with a new sample.
 
If value is confirmed, continue to withhold study drug until value returns to normal reference range or baseline value.
 

		ALT or AST $> 8 \times$ ULN	
 
Interrupt study drug dosing and redraw lab with a new sample.
 
If value is confirmed, discontinue study drug and complete supplemental hepatic eCRF.
 

		ALT or AST $> 5 \times$ ULN	
 
Interrupt study drug dosing and redraw lab with a new sample.
 
If value is confirmed for <math>> 2</math> weeks of duration, discontinue study drug and complete supplemental hepatic eCRF.
 

		ALT or AST $> 3 \times$ ULN	
 
Interrupt study drug dosing and redraw lab with a new sample.
 
If value is confirmed and patient has appearance of fatigue, nausea, vomiting, right upper quadrant pain or tenderness, fever, rash, and/or eosinophilia (<math>> 5\%</math>) discontinue study drug and complete supplemental hepatic eCRF.
 
If value is confirmed and total bilirubin <math>> 2 \times</math> ULN or international normalized ratio (INR) <math>> 1.5</math>, discontinue study drug and complete supplemental hepatic eCRF.
 

	Serum Creatinine	$> 1.5 \times$ the baseline value and $>$ ULN	
 
Interrupt study drug dosing and redraw lab with a new sample.
 
If value is confirmed, continue to withhold study drug until value returns to normal reference range or baseline value.
 

		$\geq 2$ mg/dL	
 
Interrupt study drug dosing and redraw lab with a new sample.
 
If value is confirmed, continue to withhold study drug until value returns to normal reference range or baseline value.
 

	ALT or AST	$> 5 \times$ ULN	
 
Interrupt study drug dosing and redraw lab with a new sample.
 
If value is confirmed, send HBV DNA by PCR.
 
If HBV DNA by PCR is positive, discontinue study drug and complete supplemental hepatic eCRF.
 

Subjects who are HBc Ab+ and HBV DNA negative at Screening			

## 6.3 Data Monitoring Committee

---

An internal DMC will review safety data. A separate DMC charter will be approved before the first subject is enrolled into the study. The DMC is responsible for monitoring safety data, alerting AbbVie to possible safety concerns related to the conduct of the study, and recommending appropriate actions for study conduct and management.

# 7 STATISTICAL METHODS & DETERMINATION OF SAMPLE SIZE

## 7.1 Statistical and Analytical Plans

---

Complete and specific details of the statistical analysis will be described and fully documented in the Statistical Analysis Plan (SAP). The SAP will be finalized prior to the Week 12 database lock for the primary analysis. The statistical analyses will be performed using SAS (SAS Institute Inc., Cary, North Carolina, USA).

## 7.2 Definition for Analysis Populations

---

The Full Analysis Set (FAS) includes all enrolled subjects who received at least 1 dose of ravagalimab (including subjects randomized to ravagalimab prior to Version 4.0). The FAS will be used for all efficacy and baseline analyses.

Subjects enrolled prior to version 4.0 will be unblinded after they finish Week 8 assessments. Subjects who were randomized to and received ravagalimab will be included in the FAS.

The Safety Analysis Set consists of all subjects who received at least 1 dose of study drug. Subjects randomized to the study prior to Version 4.0 will be analyzed along with subjects enrolled after Version 4.0 for safety analysis. Subjects will be grouped based on the treatment received.

Depending on the magnitude of missing data due to COVID-19, additional appropriate analysis may be performed with details included in the SAP.

## 7.3 Statistical Analyses for Efficacy

---

### Primary Analysis

The primary analysis will be performed after all subjects completed the study induction period (i.e., completed Week 12 assessments). The final analysis will be performed after all subjects completed the study maintenance period. Additional analysis may be performed to support program development or health authority requests. There will be no multiplicity test alpha-adjustment for this proof of concept study.

The primary efficacy endpoint is the proportion of subjects with endoscopic improvement at Week 8. The null hypothesis is that there is no difference in the proportion of subjects with endoscopic improvement at Week 8 between ravagalimab treated subjects and historical placebo.

Analysis of the primary efficacy endpoint will be conducted on the FAS. Comparison of the primary efficacy endpoint will be performed between the ravagalimab group and the historical placebo group using Bayesian approach with placebo distribution as [REDACTED] from historical data meta-analysis and prior for ravagalimab Beta (0.5, 0.5), the Jeffrey's prior for binomial distribution. The placebo prior is determined based on available placebo data from similar trials and may be updated if new placebo data from similar trials become available before the primary analysis database lock.

Non-Responder Imputation while incorporating Multiple Imputation to handle missing data due to COVID-19 (NRI-C) will be applied to the primary endpoint analysis.

Details on the primary, secondary, and other efficacy analyses are provided in the SAP.

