#### **Induction Period**

Up to approximately 40 subjects will be enrolled in the induction period to receive the following treatment:

- Ravaglimab 600 mg intravenous (IV) Week 0; ravaglimab 300 mg subcutaneous (SC) Weeks 2, 4, 6, 8, and 10.

Once the 30th subject completes Week 8 assessments an interim analysis will occur. This interim analysis will inform the planning of future Phase 2b and 3 studies. Enrollment into the induction period may continue until approximately 40 subjects have enrolled, or enrollment may be terminated if the study objectives are determined to have been met.

An endoscopy is required at Screening, and evaluation of endoscopic improvement will occur at Week 8. In order to explore the time-course of ravaglimab efficacy, subjects will continue through Week 12 and

will be assessed for clinical response per Partial Adapted Mayo score at Week 12. Subjects who complete the induction period and achieve clinical response per Partial Adapted Mayo score at Week 12 will be given the opportunity to continue into the maintenance period. Subjects not achieving clinical response per Partial Adapted Mayo score at Week 12 will be discontinued and have a follow-up visit (or call if a visit is not possible) 84 days from the last dose of study drug to obtain information on any new or ongoing AEs.

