### Interim Analysis

An interim efficacy analysis will be performed after approximately 30 subjects complete Week 8 assessments. This interim analysis will inform the planning of future Phase 2b and 3 studies. Enrollment into the induction period will continue until approximately 40 subjects have been enrolled.

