### Sample Size Estimation and Decision Probability

The planned sample size is up to approximately 40 subjects.

Meta-analysis for historical placebo data from tofacitinib (OCTAVE1/2), upadacitinib (Phase 2b; data on file) and ustekinumab (UNIFI) studies gives [REDACTED] endoscopic improvement rate at Week 8. The matched prior distribution for placebo is [REDACTED]. The prior for ravagalimab treatment group will be set to Jeffreys prior Beta (0.5, 0.5) as non-informative. The probability that the posterior probability of rate difference  $> 0$  is larger than 90% is more than 90% if the endoscopic improvement rate difference is 25% between ravagalimab and historical placebo, given a sample size of 40 subjects for ravagalimab. If ravagalimab has the same endoscopic improvement rate of [REDACTED] as historical placebo, that probability is approximately 3.1%.

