11.0 Interim Analyses

After 30 ongoing subjects complete Week 8 assessments, an interim analysis will be performed in order to explore if proof of concept has already been demonstrated. This interim analysis will inform the planning of future Phase 2b and 3 studies. Enrollment into the induction period will continue until approximately 40 subjects have been enrolled. For this proof of concept study, no alpha adjustment will be conducted for this interim analysis.

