Prior to the database lock for the interim analysis, Upadacitinib UC Phase 3 study data became available. This Phase 3 study has the same population, inclusion and exclusion criteria with Upadacitinib UC Phase 2b study as shown in [Table 5](#).

- Tofacitinib Phase 3
 - OCTAVE – Induction 1 (4/65)
 - OCTAVE – Induction 2 (4/65)
- Stelara Phase 3 UNIFI – Induction (11/161).
- [REDACTED]
- [REDACTED]

A historical rate of [REDACTED] is obtained based on the meta-analysis, see [Figure 3](#) as below. The prior distribution was updated to [REDACTED]. Primary analysis will be conducted using this prior distribution for placebo.

Figure 3. Meta-analysis of Updated Historical Placebo Rate (including Upadacitinib UC Phase 3)

A large black rectangular redaction box covers the area where Figure 3 would have been located.

Historical rates for secondary endpoints at Week 8 are summarized in [Table 6](#) below.

Table 6. Historical Placebo Data for Secondary Endpoints

Endpoints	Historical Data					[REDACTED]	[REDACTED]
	OCTAVE-1/2	Stelara Ph3	[REDACTED]	[REDACTED]	[REDACTED]		
Clinical remission per Adapted Mayo score	NA	NA	[REDACTED]	[REDACTED]	[REDACTED]	[REDACTED]	[REDACTED]
Clinical response per Adapted Mayo score	NA	NA	[REDACTED]	[REDACTED]	[REDACTED]	[REDACTED]	[REDACTED]
Clinical response per Partial Adapted Mayo score	NA	NA	[REDACTED]	[REDACTED]	[REDACTED]	[REDACTED]	[REDACTED]
Clinical remission per Full Mayo score	NA	2/161	[REDACTED]	[REDACTED]	[REDACTED]	[REDACTED]	[REDACTED]
Endoscopic remission	NA	NA	[REDACTED]	[REDACTED]	[REDACTED]	[REDACTED]	[REDACTED]

[figure not shown]
NA = data are not applicable in subpopulation for respective endpoints.

Note that these five trials above enrolled a mixed population of subjects with anti-TNF-naïve or anti-TNF-IR, Bio-IR or non Bio-IR. Only Bio-IR subgroup data was used from these studies with mixture population.

D2. Prior Distribution Determination

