Prior to enrollment completion, the study team and the independent statistician will meet as needed and agree on the final propensity score analysis rules (for example, matching ratio, matching caliper) of each step. Any question (must be unrelated to treatment assignment information) from the independent statistician will also be addressed during these meeting(s).

After Study M15-722 enrolled 40 subjects, the input datasets will be delivered to the independent statistician for propensity score estimation and matching, without accessing the subject-level post-baseline data (including primary endpoint data) of selected historical placebo subjects and Study M15-722 subjects. The independent statistician will

check the covariate balance before and after matching is performed to make sure the balance is improved following the matching.

5. Final covariate datasets

The resultant datasets (matched) containing subject-level covariate data will be delivered by the independent statistician to the study team prior to the primary database lock for analysis. Matched datasets should discard those unmatched subjects. The analysis-ready datasets should include variables such as re-identified subject ID, baseline characteristics, propensity score.

There is no plan to share interim data with external experts or with Regulatory Agencies (prior to study completion and availability of final study results).

6. Final data analysis

After database lock, the study programming team will merge the final output datasets with datasets containing post-baseline data of ravaglimab and historical placebo subjects and perform the pre-specified analyses.

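### The placebo prior may still be changed after the open-label interim efficacy analysis, and the matching rules for the additional propensity analysis have no pre-interim cut-off

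*Protocol*

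**What the plan says.** **Prior.** The primary analysis compares ravagalimab, under a Beta(0.5, 0.5) prior, with a placebo distribution taken from a meta-analysis of earlier trials. Protocol 7.3 (Primary Analysis) adds that the placebo prior "may be updated if new placebo data from similar trials become available before the primary analysis database lock". The same section, under Interim Analysis, states: "An interim efficacy analysis will be performed after approximately 30 subjects complete Week 8 assessments". SAP 11.0 says the interim is done "in order to explore if proof of concept has already been demonstrated". Protocol 4.1 (Induction Period) adds that "enrollment may be terminated if the study objectives are determined to have been met". On the SAP, Protocol 7.1 says: "The SAP will be finalized prior to the Week 12 database lock for the primary analysis".

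SAP 3.0, dated 10 February 2021, has already used the permission. Appendix D1 records: "Prior to the database lock for the interim analysis, Upadacitinib UC Phase 3 study data became available". It then updates the prior and names the updated one for the primary analysis. The version history in SAP 13.0 keeps the protocol's prior as a sensitivity analysis.

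**Matching.** The propensity analysis appears only in the SAP (8.3.5 and Appendix E), as an additional analysis. It starts from 1:1 greedy matching with a caliper of 0.2 and a set of starred mandatory covariates. Other ratios and calipers may be considered, and the remaining covariates are optional. Appendix E4 has the study team and an independent statistician settle the details before the 40th subject's first dose. Step 4 of the same appendix has them "agree on the final propensity score analysis rules (for example, matching ratio, matching caliper" before enrollment is complete.

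**The concern.** With no concurrent control, the placebo prior is the whole comparator for the primary analysis. The study is open label, and at the interim roughly 30/40 = 75% of the planned primary-endpoint outcomes will have been analysed. Between that analysis and the primary lock, the protocol still allows the comparator to change. It does not say who decides, which trials count as similar, or that a decision must precede the interim results. Neither document describes a barrier inside the sponsor between the interim results and those who would update the prior. SAP Appendix E4 rules out sharing interim data with external experts and regulators, which is a different matter.

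The false-positive probability of about 3.1% in Protocol 7.3 is computed for a prior fixed independently of the trial's data. If the prior may be chosen once most outcomes are known, that figure no longer describes the procedure.

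The matching rules raise the same issue on a smaller scale. The independent statistician has no post-baseline data. The study team that agrees the rules works on an open-label trial and keeps the historical placebo outcomes.

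**Working it through.** **Inputs from the documents.** Ravagalimab prior Beta(0.5, 0.5); N = 40 ("The planned sample size is up to approximately 40 subjects"); a threshold of 90% for the posterior probability that the difference exceeds 0, used for the operating characteristics; effect of 25 percentage points; 20 or fewer historical subjects borrowed (SAP Appendix D2). Disclosed placebo counts are 4/65 + 4/65 + 11/161 = 19/291 = 6.5%. The fourth trial contributes 325 − 291 = 34 subjects, with its responders redacted.

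**Assumed, because redacted.** Placebo prior Beta(20m, 20(1 − m)), that is, a weight of 20 subjects and mean m; true placebo rate 6%.

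**Method.** Find the smallest r for which P(Beta(0.5 + r, 40.5 − r) > Beta(20m, 20(1 − m))) > 0.90. The false-positive rate is then P(Binomial(40, 0.06) ≥ r).

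**The plan's own figure.** With m = 6%, the prior is Beta(1.2, 18.8). The posterior probability is 0.859 at 5/40 and 0.906 at 6/40, so r = 6. Then P(Binomial(40, 0.06) ≥ 6) = 0.0309, which agrees with 3.1%. Power at 6% + 25% = 31% is 0.994, which agrees with more than 90%. The match is not unique: by the binomial tail alone, 4.4% with r = 5 or 7.7% with r = 7 also gives 3.1%. It is therefore consistent with the plan but does not identify the prior.

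**Moving the prior mean (weight 20, true rate 6%).**

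| Prior mean | Responders needed of 40 | False-positive rate |
|---|---|---|
| 3% | 4 | 21.7% |
| 4–4.5% | 5 | 9.0% |
| 5–6% | 6 | 3.1% |
| 6.5–7% | 7 | 0.9% |
| 8% | 8 | 0.2% |

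The weight matters too. At a mean of 6%, weights of 10 and 15 need 7 of 40, and a weight of 20 needs 6.

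**What interim knowledge adds.** Suppose 4 of 30 have responded and the true rate is 6%. If 6 are needed, at least 2 of the last 10 must respond: 1 − 0.94¹⁰ − 10 × 0.06 × 0.94⁹ = 0.118. If 5 are needed, at least 1 must: 1 − 0.94¹⁰ = 0.461.

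**Order of events.** The interim needs Week 8 data on about 30 subjects; the primary lock needs Week 12 data on all. The prior's window therefore extends past the interim. The 40th first dose and the end of enrollment may fall before or after it, because neither is tied to it. If enrollment stops short of 40, as Protocol 4.1 allows, the 40th-dose deadline never arrives.

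**The case against.** **A reader might infer that the prior was chosen in the light of interim results.** The documents do not show this. SAP Appendix D1 says the new placebo data were available before the interim lock, SAP 11.0 describes the interim as still to come, and the protocol's prior is retained as a sensitivity analysis. The direction of the update is redacted, so it may have raised the bar. The trigger is also external: new placebo data from similar trials. This answers any suggestion of misuse, but it leaves the permission open.

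**A reader might infer that the matching rules can move the primary result.** They cannot. The primary comparison is the Bayesian one in SAP 8.3.3. The stated reasons for changing ratio or caliper are balance and retained sample size, which do not involve outcomes. Questions from the independent statistician must be unrelated to outcomes, at least as the opening of Appendix E4 puts it; step 4 repeats the limit without the outcome clause. What stands is narrower: those who agree the rules are not shielded.

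**A reader might infer that any shift of a point or so in the prior mean multiplies the error rate.** It does not. Means of 5%, 5.5% and 6% all need 6 of 40, and upward moves from 6% never raise the error rate. Inflation needs a fall to about 4.5%. With 0 to 2 responders assumed in the redacted 34-subject trial, simple pooling gives 19/325 = 5.8% to 21/325 = 6.5%. Reaching 4.5% would then take 19/0.045 − 325 ≈ 97 to 21/0.045 − 325 ≈ 142 new placebo subjects with no responder. That ignores the redacted Phase 3 data and the meta-analysis weighting, but it shows that such a move would not be routine. And if the true rate equals the prior mean each time, the false-positive rate at weight 20 stays between 1.3% and 3.6% for means of 4.5–8%.

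**No success rule remains.** The protocol's summary of changes records removal of the proof-of-concept criterion, so 90% describes operating characteristics and binds nothing. This lowers the stakes. The posterior probability is still the primary output, and the operating characteristics are still quoted to support the design.

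**Conclusion.** The point holds as an open permission. The primary placebo prior may be changed after the open-label interim, and SAP 3.0 names a prior without closing that window. Separately, and only for an additional analysis, the matching ratio, caliper and optional covariates can be settled after the interim by a team that is not shielded from outcomes.

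The size can only be illustrated. Under the assumed weight and true rate, one step in the boundary, from 6 to 5 of 40, changes the false-positive rate from 3.1% to 9.0%; a step to 7 gives 0.9%. Some changes of prior cross a boundary and others do not. This does not void the stated operating characteristics: they stand for a prior fixed before the interim, and the present text does not guarantee one. It is worth correcting before the interim lock, but in an exploratory study with no binding success rule it does not undermine the design.

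**What to change.** In Protocol 7.3 and SAP 8.3.3, state that the placebo prior in SAP 3.0 is final for the primary analysis as of the interim database lock, and that placebo data appearing later enter sensitivity analyses only.

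In SAP Appendix E4, fix the 1:1 ratio, the 0.2 caliper and the covariate list before the interim lock, replacing the two present deadlines. Any later change would be made by the independent statistician alone, on covariate balance and number of matches, and documented.

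The cost is a few sentences, with no new data or subjects. The downside is that placebo data arriving after the interim lock inform sensitivity analyses only, even if they are better than those in the prior.

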### Interim Analysis

An interim efficacy analysis will be performed after approximately 30 subjects complete Week 8 assessments. This interim analysis will inform the planning of future Phase 2b and 3 studies. Enrollment into the induction period will continue until approximately 40 subjects have been enrolled.

### Sample Size Estimation and Decision Probability

The planned sample size is up to approximately 40 subjects.

Meta-analysis for historical placebo data from tofacitinib (OCTAVE1/2), upadacitinib (Phase 2b; data on file) and ustekinumab (UNIFI) studies gives [REDACTED] endoscopic improvement rate at Week 8. The matched prior distribution for placebo is [REDACTED]. The prior for ravagalimab treatment group will be set to Jeffreys prior Beta (0.5, 0.5) as non-informative. The probability that the posterior probability of rate difference  $> 0$  is larger than 90% is more than 90% if the endoscopic improvement rate difference is 25% between ravagalimab and historical placebo, given a sample size of 40 subjects for ravagalimab. If ravagalimab has the same endoscopic improvement rate of [REDACTED] as historical placebo, that probability is approximately 3.1%.

